1.4 The variability in clinical phenotype among patients

Despite comparable coagulation factor activities in each category of severity, differences in clinical phenotypes have been described. Studies have shown that roughly 9-15% of patients with severe haemophilia have been described to have a very mild phenotype with few joint bleeding and almost absent joint damage. [51-56]

Clotting time assays such as PT and aPTT only measure the first part of the coagulation pathway, namely, the initiation phase until the formation of a visible fibrin clot. Therefore, they do not give a comprehensive overall picture of the clotting system. The utilization of global clotting assays may provide more accurate evaluation of an individual's in vivo haemostatic state and response to treatment. [57, 58]

In the HiN-6 study, we will evaluate two global haemostasis assays; the Calibrated Automated Thrombogram (CAT) assay and the Nijmegen Haemostasis Assay (NHA). It is expected that these assays will better reflect the patients' clinical phenotype. If proven useful, these assays can be helpful in guiding individual dose tailoring as part of a more personalised treatment strategy.

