6.4 Studies elucidating the variability in clinical phenotype among PWH

6.4.1 To assess the usefulness of The Calibrated Automated Thrombogram (CAT) assay in relation to clinical phenotype.

Primary objective 1: To establish specific sample conditions to generate reliable CAT assay outcome parameters in patients with haemophilia.

Study design and population: In vitro spiking experiments will be used to establish specific sample conditions to generate reliable CAT assay outcome parameters. Thrombin Generation (TG) in FVIII or FIX deficient plasma is determined after in vitro suppletion of FVIII or FIX in final activity of 5%, 10%, 15%, 20%, 25%, 30%, 35%, 40%, 45% and 50% to establish maximum TG parameters. Optimal TG

HiN-6 study

conditions are studied by varying the amount of TF: 5pM, 1pM and 0,5 pM. Final phospholipid concentration is set at 4 uM. Cases will consist of 25 severe haemophilia patients, 25 moderate haemophilia patients and 25 mild haemophilia patients. Controls will consist of 25 healthy patients without haemophilia and no personal or family history of thrombosis or bleeding disorders and no relevant medication.

Secondary objective 1: To assess the association between the results of the CAT assay and the self-reported clinical bleeding phenotype of patients with severe, moderate and mild haemophilia.
Study design and population: A cross-sectional study design will be used. The population will consist of 25 severe haemophilia patients, 25 moderate haemophilia patients and 25 mild haemophilia patients.

Determinant: The following parameters of the CAT assay will be used as the determinant; lag-time, time to peak, peak height and endogenous thrombin potential.

Endpoint: The modified bleeding severity score developed by Schulman et al [97] will be used as the endpoint (see paragraph 5.1.3).

Statistical analysis: The association between each parameter of the CAT assay (lag-time, time to peak, peak height and endogenous thrombin potential) and bleeding severity will be assessed using linear regression.

Secondary objective 2: To evaluate if the CAT assay can accurately diagnose the self-reported clinical bleeding phenotype of patients with severe, moderate and mild haemophilia.

Study design and population: A cross-sectional study design will be used. The population will consist of 25 severe haemophilia patients, 25 moderate haemophilia patients and 25 mild haemophilia patients.

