Determinants: The following parameters of the CAT assay will be used as determinants; lag-time, time to peak, peak height and endogenous thrombin potential. FVIII concentration (measured using the chromogenic assay) will also be used as a determinant.

Endpoint: The modified bleeding severity score developed by Schulman et al [97] will be applied to this study population (see paragraph 5.1.3) and used as a dichotomous outcome. Mild bleeders will be defined as being in the lowest two quartiles of the modified bleeding severity score, severe bleeders will be defined as being in the highest two quartiles of the modified bleeding severity score. **Statistical analysis:** The CAT assay parameters and FVIII concentration will be used to predict if a patient is a mild or a severe bleeder (based on the modified bleeding severity score). We will quantify diagnostic performance by constructing ROC-curves for each parameter of the CAT assay

and for FVIII concentration. We will then test if the AUROC of each parameter of the CAT assay differs significantly from the AUROC of the chromogenic assay. This analysis will be performed for the total population and separately for each category of severity.

6.4.2 To assess the usefulness of the Nijmegen Haemostasis Assay (NHA) in relation to clinical phenotype:

Primary objective 1: To assess the association between the results of the NHA and the self-reported clinical bleeding phenotype of patients with severe, moderate and mild haemophilia A and B.
Study design and population: A cross-sectional study design will be used. The population will consist of all haemophilia A and B patients in the Netherlands.

Determinant: The following parameters of the NHA will be used as determinants; lag-time, thrombin peak-time, thrombin peak-height, area under the curve (AUC), fibrin lysis time (FLT), plasmin peak-height and plasmin potential.

Potential confounders: FVIII/FIX genotype, VWF antigen levels and VWF activity.

Endpoint: The modified bleeding severity score developed by Schulman et al [97] will be used as the endpoint (see paragraph 5.1.3). **Statistical analysis:** The association between each parameter of the NHA and bleeding severity will be assessed using linear regression.

Primary objective 2: To evaluate if the NHA can accurately diagnose the self-reported clinical bleeding phenotype of patients with severe, moderate and mild haemophilia.

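### The CAT and NHA association regressions omit factor activity, so their crude coefficients cannot show that either assay explains bleeding differences at comparable factor level

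*Protocol*

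**What the plan says.** **NHA (6.4.2, primary objective 1).** The outcome is the modified bleeding severity score of section 5.1.3. The analysis sentence is "The association between each parameter of the NHA and bleeding severity will be assessed using linear regression", for seven assay parameters. On who is analysed: "The population will consist of all haemophilia A and B patients in the Netherlands". On adjustment: "Potential confounders: FVIII/FIX genotype, VWF antigen levels and VWF activity". The analysis sentence does not say whether even these variables enter the model.

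**CAT (6.4.1, secondary objective 1).** "The association between each parameter of the CAT assay" and the same score is assessed by linear regression, for four parameters. The sample is "25 severe haemophilia patients, 25 moderate haemophilia patients and 25 mild haemophilia patients", analysed together. No confounder is listed.

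**Rationale (1.4).** "Despite comparable coagulation factor activities in each category of severity, differences in clinical phenotypes have been described". The Summary gives the same motivation.

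**Elsewhere in the protocol.** Section 6.5.1, secondary objective 3, uses the same bleeding score and names haemophilia severity as a potential confounder. Section 6.1.2, objective 2, adjusts a bleeding analysis for age and severity.

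**The concern.** Both sides of these regressions can be expected to move with factor activity. Section 1.4.2 reports that thrombin generation is severely diminished in severe haemophilia A, and the CAT work in 6.4.1 sets its conditions by adding FVIII or FIX to deficient plasma. On the outcome side, one of the two components of the score is annual factor consumption per kg, scaled to roughly the maximum of regular prophylaxis (5.1.3).

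When severe, moderate and mild patients are pooled without factor activity in the model, an assay that is only a noisy re-measurement of factor activity will tend to appear associated with bleeding. That result would not bear on why patients with similar factor levels bleed differently. Section 1.4 says that these assays, if proven useful, could support individual tailoring of treatment, so a coefficient that merely reflects factor level should not be read as evidence of usefulness.

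**Working it through.** **Inputs from the protocol.** CAT: 25 + 25 + 25 = 75 patients. Whole study: 1800 × 0.70 = 1260, which reproduces the figure in section 4.4. Severity classes as in section 4.1. No alpha, power or effect size is stated for these regressions.

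**Assumptions.** A two-sided 5% level; the correlations of assay and score with log factor activity; the severity mix for NHA. The correlations are shown as ranges.

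**Set-up.** Suppose that assay and score are independent given factor activity, so that the assay adds nothing. The crude correlation is then the product

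r = r(assay, activity) × r(score, activity).

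By the Fisher z approximation, with s = atanh(r) × √(n − 3),

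P(reject) = Φ(s − 1.96) + Φ(−s − 1.96).

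- CAT, both correlations 0.3: r = 0.09, s = 0.0902 × √72 = 0.77, P = 12%.
- CAT, both 0.5: r = 0.25, s = 0.2554 × √72 = 2.17, P = 58%.
- CAT, both 0.7: r = 0.49, s = 0.5361 × √72 = 4.55, P = 99.5%.
- NHA, n = 1260, both 0.3: r = 0.09, s = 0.0902 × √1257 = 3.20, P = 89%. At 0.5 and 0.7, P = 100%.

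**Simulation of the regressions.** Activity was drawn uniformly within class (0.002-0.01, 0.01-0.05 and 0.05-0.40 IU/ml). CAT had 4000 runs. NHA had 2000 runs at n = 1260, with an assumed 40/15/45% severe/moderate/mild split. The genotype proxy assumes a null mutation in 80% of severe and 5% of other patients. Entries are rejection rates with both correlations at 0.3 / 0.5 / 0.7.

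| Model | CAT, n = 75 | NHA, n = 1260 |
|---|---|---|
| Crude | 13% / 59% / 99.9% | 90% / 100% / 100% |
| Plus genotype proxy | 9% / 30% / 93% | 45% / 100% / 100% |
| Plus severity class | 6% / 6% / 11% | 6% / 15% / 72% |
| Plus log factor activity | 6% / 5% / 5% | 5% / 5% / 5% |

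A second simulation varied the two links separately. For CAT, with activity explaining 10% of score variance and assay correlations of 0.3 / 0.5 / 0.7, crude rejection was 13% / 27% / 48%. With 25% explained it was 25% / 60% / 91%, and with 50% explained 47% / 92% / 100%. For NHA at n = 1000, correlation 0.3 and 10% explained, it was 84%.

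**Reading.** The listed genotype adjustment reduces the problem for NHA but does not remove it. Severity class alone does not restore the nominal level when the correlations are strong. Continuous activity does in this set-up, partly by construction, because the model adjusts for the exact variable that generated both quantities.

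**The case against.** **The objective may be the crude association.** The comparable-activity wording stands in the Summary and in 1.4. Section 2.4 speaks only of variability in phenotype, and each association objective is framed across severe, moderate and mild patients. Read literally, an unadjusted regression answers that, and no hypothesis test is stated. This stands: the crude estimate is not invalid as description. It does not serve the rationale, and 6.5.1 treats severity as a potential confounder of the same score.

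**Value beyond factor level has its own objective.** A reader might infer that the protocol never examines it. That is not so. CAT secondary objective 2 compares the AUROC of each parameter with that of chromogenic FVIII, overall and within each severity class. NHA primary objective 2 adds the assay to a FVIII model with bootstrap validation. The cover is partial. The CAT step is a head-to-head comparison, not a joint model, and has 25 patients per class. The NHA base model holds FVIII only although haemophilia B is included. Both use a score split at the median.

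**The size rests on assumptions.** A reader might also infer that these regressions are bound to come out positive. For CAT with weak correlations the rate is 12-13%, so that goes too far.

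**Covariates may be settled in an analysis plan that is not shown.** This is possible, since the list is headed as potential confounders. But the protocol chose a set for NHA and left out the most obvious member.

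**Adjustment changes the estimand, and activity may be coarse.** Factor level acts on bleeding through thrombin generation, so the adjusted coefficient answers a different question; that is why both should be shown. Section 4.1 defines severe only as below 0.01 IU/ml. If activity is not resolved below that, adjustment behaves more like class adjustment in severe patients.

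**Conclusion.** The point holds in a limited form. Both association analyses omit factor activity, and the crude coefficients cannot show that either assay explains phenotype variability at comparable factor activity. Should the assay carry nothing beyond factor activity, a crude 5% test would reject in about 12-100% of cases for CAT (n = 75) and about 84-100% for NHA (n about 1000-1260). These figures rest on an assumed alpha, assumed correlations of about 0.3-0.7 and an assumed severity mix. Blood sampling is voluntary, so the NHA sample may be below 1260; at n = 1000 the conclusion is the same.

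The defect is confined to the two association objectives, one of which is a primary objective of its substudy. The documents do not support the stronger readings that section 2.4 itself poses the comparable-activity question, that a positive finding is inevitable, or that the second objectives offer no protection.

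**What to change.** In 6.4.1 secondary objective 1 and 6.4.2 primary objective 1, add continuous log baseline activity of the deficient factor (FVIII in haemophilia A, FIX in haemophilia B) as a covariate. Report the adjusted coefficient as the result that addresses phenotype beyond factor level, and give the crude coefficient beside it, labelled descriptive. Severity class may be added but is not sufficient alone. Where activity in severe patients is not resolved below 0.01 IU/ml, acknowledge residual confounding.

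The cost is about one sentence per section, one or two degrees of freedom, and a smaller reported association. Factor activity is among the laboratory tests named in 5.1.2, and baseline values are taken from the records under 5.1.3. The case report form allows these to be unknown, so completeness should be checked.

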Study design and population: A cross-sectional study design will be used. The population will consist of all haemophilia A and B patients in the Netherlands.

Determinants: The following parameters of the NHA will be used as determinants; lag-time, thrombin peak-time, thrombin peak-height, area under the curve (AUC), fibrin lysis time (FLT), plasmin peak-height and plasmin potential. FVIII concentration (measured using the chromogenic assay) will also be used as a determinant.

Other potential predictors of clinical bleeding phenotype: FVIII/FIX genotype, VWF antigen levels and VWF activity.

Endpoint: The modified bleeding severity score developed by Schulman et al [97] will be applied to this study population (see paragraph 5.1.3) and used as a dichotomous outcome. Mild bleeders will be defined as being in the lowest two quartiles of the modified bleeding severity score, severe bleeders will be defined as being in the highest two quartiles of the modified bleeding severity score. **Statistical analysis:** Firstly, we will perform univariate logistic regression using FVIII concentration as

the determinant (the basic prediction model). To quantify the incremental value of the NHA parameters, they will be added to the basic prediction model to create the full prediction model. For internal validation, bootstrapping techniques will be used to reduce overfitting. Agreement between observed and predicted outcomes will be assessed using a calibration plot. Discrimination will be assessed by calculating the AUROC of the full model. The added value of the NHA will be assessed by comparing the AUROC of the basic model (only FVIII concentration) with the AUROC of the full model (FVIII concentration + NHA parameters).

6.4.3 To assess misclassification of disease severity by the one-stage clotting assay in haemophilia B patients:

Primary objective 1: To assess the extent of discrepancy in FIX activity level as measured by the one stage clotting assay to the chromogenic assay in patients with mild and moderate haemophilia B.
Study design and population: A cross-sectional study design will be used. The population will consist of all persons with mild and moderate haemophilia B.

Determinant: FVIII activity level, as determined by the chromogenic assay.

Endpoint: FVIII activity level, as defined using the one-stage clotting assay.

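### NHA accuracy study (6.4.2, primary objective 2): genotype and VWF are named as predictors of bleeding but enter neither model, so the AUROC gain can credit the NHA with information they already carry

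*Protocol*

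**What the plan says.** Section 6.4.2, primary objective 2, asks whether the NHA can identify mild and severe bleeders, split at the median of the modified bleeding severity score. Besides the NHA parameters and FVIII concentration it names a third group of variables: "Other potential predictors of clinical bleeding phenotype: FVIII/FIX genotype, VWF antigen levels and VWF activity".

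The analysis text then fixes both models. The basic model is a univariate logistic regression on FVIII concentration. For the full model: "To quantify the incremental value of the NHA parameters, they will be added to the basic prediction model to create the full prediction model". Added value is read from "comparing the AUROC of the basic model (only FVIII concentration) with the AUROC of the full model (FVIII concentration + NHA parameters". Bootstrapping and a calibration plot accompany this.

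Primary objective 1 of the same section, on the association between the NHA and bleeding severity, lists the same variables in another role: "Potential confounders: FVIII/FIX genotype, VWF antigen levels and VWF activity". No other part of the protocol gives them a role in primary objective 2.

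**The concern.** An increment is always an increment over something. The protocol names three variables that may predict the outcome and leaves them out of the model against which the NHA is judged. In primary objective 1 it also treats them as possible confounders, that is, as variables that may be related to both the assay and bleeding. If they are, the NHA parameters act partly as stand-ins for them in the full model.

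At stake is how a positive result is read. Section 1.4 says that these assays, if proven useful, could help to guide individual dose tailoring. An assay that repeats what genotype and VWF already tell is worth less for that purpose than one that adds to them, and the planned comparison cannot tell the two apart.

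This is not a detail left open for a statistical analysis plan. The protocol states the content of both models and the comparison between them.

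**Working it through.** **1. The role of the three variables, place by place**

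| Place | Role given | In the stated model? |
|---|---|---|
| 6.4.2, primary objective 1 | potential confounders | linear regression stated without naming them |
| 6.4.2, primary objective 2 | other potential predictors | no: both models are spelled out without them |
| 6.5.1, secondary objective 3 (same bleeding score) | potential adjustment for FVIII genotype and VWF | adjustment foreseen |

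**2. Why the omission can matter**

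Let F be FVIII concentration, Z the combined genotype/VWF signal and N an NHA parameter without any effect of its own:

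- logit P(severe bleeder) = a + b_F·F + b·Z
- N = c·F + λ·Z + noise

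If Z is left out, N helps to predict Z at given F whenever λ ≠ 0, and so helps to predict bleeding whenever b ≠ 0 as well. If b = 0 or λ = 0 there is no credit. With Z in both models, N adds nothing in truth.

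**3. Inputs**

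- Sample size (section 4.4): 1800 × 0.70 = 1260, which reproduces the protocol's figure. Blood sampling is voluntary (5.1.2), so the NHA set may be smaller.
- Seven NHA parameters (6.4.2): "lag-time, thrombin peak-time, thrombin peak-height, area under the curve (AUC), fibrin lysis time (FLT), plasmin peak-height and plasmin potential".
- Outcome split at the median (6.4.2).
- The protocol gives no effect sizes. Assumed: |b_F| = 1.0 log-odds per SD; |b| = 0, 0.25, 0.5 or 0.75 per SD; c = 0.5; λ = 0, 0.2 or 0.4 for each NHA parameter (unit variance, independent noise); Z built from three continuous variables for genotype, VWF antigen and VWF activity.

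**4. Results: n = 1260, 200 repetitions per setting, mean apparent AUROC gain from an NHA with no information of its own**

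| \|b\| | λ | Gain, protocol's pair | Gain, genotype and VWF in both models | Excess |
|---|---|---|---|---|
| 0.25 | 0.2 | 0.005 | 0.003 | 0.002 |
| 0.25 | 0.4 | 0.009 | 0.003 | 0.006 |
| 0.5 | 0.2 | 0.012 | 0.003 | 0.009 |
| 0.5 | 0.4 | 0.023 | 0.003 | 0.020 |
| 0.75 | 0.2 | 0.022 | 0.003 | 0.019 |
| 0.75 | 0.4 | 0.042 | 0.003 | 0.039 |
| any, with \|b\| = 0 or λ = 0 | | 0.003–0.004 | 0.003–0.004 | none |

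The 0.003–0.004 is ordinary optimism from seven extra terms, which the bootstrap is meant to remove. The excess column is not overfitting and stays after that correction. In the strongest setting the AUROCs are 0.721 (FVIII only), 0.763 (FVIII + NHA) and 0.781 (FVIII + genotype and VWF, no NHA). The apparent success of the assay is then less than the omitted variables would have given without it.

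**5. How strong the assumptions are**

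At given F, the seven parameters together recover 7λ²/(7λ² + 0.75 − λ²) of the variance of Z:

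- λ = 0.2: 0.28/0.99 = 28%
- λ = 0.4: 1.12/1.71 = 65%

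This relies on independent noise. Parameters from one assay run probably share noise and would recover less, so the upper end of the table is generous.

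**6. A simpler variant**

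One NHA parameter, NHA–VWF correlation 0.3–0.5, VWF effect 0.2–0.4 per SD on latent bleeding, n = 300 and 800. The apparent gain over FVIII alone was 0.003–0.023, and 0.000–0.002 with VWF in both models. A repeat over these ranges, with an FVIII effect of 0.8 per SD and an NHA–FVIII correlation of 0.5, gave 0.002–0.014 over FVIII alone.

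**The case against.** **A gain over FVIII alone is a coherent quantity.** This stands. Section 1.4 starts from differences in phenotype at comparable factor activity, the CAT substudy (6.4.1) also benchmarks against FVIII, and the protocol labels its basic model openly. The stated objective is diagnostic accuracy; added value is one step of its analysis. The FVIII-only comparison is therefore not wrong in itself. It misleads only if read as the gain over everything known, and the line that declares further predictors invites that reading.

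**The bias is not demonstrated.** This also stands. A reader might infer that the NHA result will be inflated. The documents do not support that: the variables are only called potential predictors and potential confounders. Section 1.4.2 does not name VWF among the things to which the assay is sensitive. Section 1.3.3 describes VWF release as raising FVIII, which is already in both models.

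**A reader might infer a high false-positive rate.** In the n = 1260 settings with both links present, a 5% likelihood-ratio test for the NHA terms rejected in 29–100% of repetitions, against 3–7% across all settings with genotype and VWF in both models. The protocol prescribes no such test; it compares AUROCs and names no test. In the one-parameter repeat, a DeLong comparison rejected in 0–14% (n = 300) and 1–66% (n = 800), where the likelihood-ratio test rejected in 12–78% and 27–99%. DeLong is conservative for nested models, so neither set gives the error rate of the planned analysis.

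**A reader might infer that the clinic already holds this information for every patient.** It may not. Genotype and VWF are extracted from records (5.1.3), but the case report form allows genotype to be not known and VWF to be unknown (items 1.5, 1.10, 1.11). Its instructions ask for the last assay, which need not match the NHA sample in time. The laboratory tests listed in 5.1.2 include FVIII genotype if unknown, but name no VWF assay.

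**Conclusion.** The point holds in conditional form. The text is clear: three predictors are declared for this objective and excluded from both models by which the NHA is judged. The AUROC difference can therefore credit the NHA with information that genotype and VWF carry, and neither the bootstrap nor the calibration plot would show it.

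This needs both links: genotype or VWF must predict bleeding given FVIII, and the NHA parameters must correlate with them given FVIII. If either is absent, the planned comparison is unharmed. Across the simulated settings with both links present, an NHA with no information of its own shows an apparent gain of about 0.002 to 0.04. That range reflects assumed coefficients and is not an estimate for this study.

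The point is worth correcting before analysis because it concerns a primary objective of the substudy and the remedy is small. It does not invalidate the comparison with FVIII alone.

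**What to change.** In section 6.4.2, primary objective 2, add a second pair of models:

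- extended basic model: FVIII concentration, genotype class, VWF antigen and/or VWF activity;
- extended full model: the same terms plus the NHA parameters.

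State that the claim of added value rests on the AUROC difference of this pair, with the same bootstrap correction. Keep the FVIII-only comparison and label it as the gain over factor level alone.

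The cost is modest. The variables are already planned for collection, so no further sampling is required. Three things need a rule:

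- missing genotype or VWF values, for example by imputation;
- the grouping of genotypes into classes, since the case report form records mutations other than the intron 22 inversion as free text and the population includes haemophilia A and B;
- VWF values that were not measured at the time of the NHA sample.

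The reported gain of the NHA may turn out smaller.

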 - o First negative inhibitor test during ITI
 - First normal recovery during ITI
 - o Confirmed inhibitor relapse after a successful ITI procedure (if positive, the

aforementioned information is also collected for the second inhibitor)

Determinants and outcomes calculated from collected data are:

• Clinical bleeding phenotype

Our score for bleeding severity is based on the bleeding severity score by Schulman et al. [97] Schulman et al also includes a joint subscore, however, we do not have this data for all patients, therefore we have decided to remove the joint subscore from the final score. Our bleeding severity score consists of 2 components; the annual joint bleed rate and annual factor consumption (corrected for bodyweight). Lastly, we will calculate the annual joint bleed rate/factor consumption using information from the HiN-6 questionnaire:

We will obtain the patient-reported annual joint bleed rate for the year 2016 using the HiN-6 questionnaire. This value is divided by 20 (which the roughly equal to the maximum number of joint bleeds that a patient without any treatment will experience). [97] This gives you a value between 0 and 1. We will obtain the patient-reported annual factor consumption for the year 2016 using the HiN-6 questionnaire. This number is divided by the mean body weight of the patient during this period. This value is then divided by 6000 (IU / kg), which is approximately the maximum consumption of regular prophylaxis. [97] This gives you a value between 0 and 1. The final score is simply the sum of the two aforementioned subscores, the score has a minimum of 0 and a maximum of 2.

• **BMI:** BMI is calculated as weight (kg) divided by height² (meters).

Chapter 6 – Substudies

This chapter describes all substudies that will be performed as part of the HiN-6 project. The objectives of the substudies are derived from the following overarching general objectives:

- 1. Describing the health status of the Dutch haemophilia population
- 2. Assessing the quality of life of PWH in the Netherlands
- 3. Assessing the quality of care of PWH in the Netherlands

- 4. Elucidating the variability in clinical phenotype among PWH
- 5. Assessing immunological mechanisms that may lead to inhibitor formation in patients with haemophilia A

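### The NHA's added value over FVIII is judged only on a bleeding score cut at the sample median, and the CAT comparison uses the same cut, which discards information for no stated reason

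*Protocol*

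**What the plan says.** Section 5.1.3 defines the score as annual joint bleeds divided by 20, plus annual factor use in IU/kg divided by 6000; "the score has a minimum of 0 and a maximum of 2".

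Section 6.4.1 (CAT), secondary objective 2, and section 6.4.2 (NHA), primary objective 2, both turn this score into two groups: mild bleeders are "defined as being in the lowest two quartiles of the modified bleeding severity score, severe bleeders" as those in the highest two. Neither place gives a reason for the cut.

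- **NHA.** A logistic model with FVIII concentration alone is extended by seven parameters: lag-time, "thrombin peak-time, thrombin peak-height, area under the curve (AUC), fibrin lysis time (FLT), plasmin peak-height and plasmin potential". "The added value of the NHA will be assessed by comparing the AUROC of the basic model" with that of the full model. Bootstrap validation and a calibration plot are planned. No significance test is named.
- **CAT.** ROC curves are built for four parameters and for FVIII. "We will then test if the AUROC of each parameter of the CAT assay differs significantly from the AUROC of the chromogenic assay".

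The uncut score is used elsewhere in section 6.4. NHA primary objective 1 and CAT secondary objective 1 relate it to each assay parameter by linear regression. The confounders listed for NHA objective 1 are genotype, VWF antigen and VWF activity. Factor level is not among them.

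**The concern.** Section 1.4 starts from the observation that patients with similar factor activity bleed differently, and it expects global assays to reflect phenotype better. What the NHA says beyond FVIII is therefore a natural core of the NHA substudy, and objective 2 is the only place where it is examined.

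A median cut treats two patients just either side of the median as opposites, and a patient just above it as equal to one at the top of the scale. The ordering within each half is thrown away. A modest true contribution of the NHA, or a modest difference between a CAT parameter and FVIII, is then easier to miss and is estimated less precisely.

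**Working it through.** **Inputs from the protocol.** Section 4.4: 1800 × 0.70 = 1260, which reproduces the stated figure. This is an upper bound for the NHA, because blood sampling is voluntary (section 5.1.2). Section 6.4.1: 3 × 25 = 75 for CAT. Seven NHA parameters are added.

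**Inputs the protocol does not give.** Alpha, power target, effect size, variance explained by factor level, and shape of the score. I assume two-sided alpha 0.05 and vary the rest.

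**Step 1: information kept.** For a normal outcome and small effects, the efficiency of a median cut relative to the full scale is φ(0)² / (0.5 × 0.5) = (1/2π) / (1/4) = 2/π = 0.637. So 1260 × 0.637 ≈ 802 and 75 × 0.637 ≈ 48. About 36% of the information is lost.

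**Step 2: power of a joint test of seven parameters.** Noncentrality on the full score is λ = N·r²/(1 − r²), with r² the share of remaining variance explained by the NHA; after the cut it is 0.637·λ. Both are referred to a noncentral chi-square with 7 df. Whatever N is, 50% power becomes 32%, 80% becomes 57%, 90% becomes 69% and 99% becomes 91%.

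At N = 1260 (for example r² = 1.15%: λ = 1260 × 0.0115/0.9885 = 14.7, after the cut 9.3):

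| r² | full score | median cut | loss (points) |
|---|---|---|---|
| 0.5% | 39.9% | 25.4% | 14.5 |
| 1.15% | 81.0% | 57.8% | 23.2 |
| 2% | 97.8% | 85.8% | 11.9 |
| 3% | 99.9% | 97.3% | 2.6 |
| 5% | about 100% | about 100% | 0.0 |

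**Step 3: simulation at N = 1260, normal score.** With factor level explaining 10% to 50% of the score and r² of 0.5% to 2%, a likelihood-ratio test on the cut score loses about 13 to 38 points against an F-test on the full score; a DeLong test of the two AUROCs loses about 18 to 50. At r² = 5% the losses are 0 to 1 and 1 to 3. Part of the DeLong loss comes from the test and not the cut. With factor level at 50% and r² = 1.5%, the two tests on the same cut outcome have 54% and 42% power, against 92% on the full score.

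**Step 4: shape of the score.**
- Lognormal score (factor level 50%, r² = 1.5%): plain linear regression 50%, likelihood-ratio test on the cut score 56%, linear model on rank-normalised scores 92%. With strong skew, plain linear regression is no better than the cut; a rank-based analysis is.
- Share of patients at zero (factor level 30%, linear regression on the uncut score against the cut): with 30% at zero the loss is 19 points at r² = 1.15% (75% to 56%) and 16 at 2% (95% to 80%). With 50% at zero it is 11 and 7. With 60% at zero there is none (45% against 50%, and 79% against 81%).

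**Step 5: CAT, N = 75, two markers compared head to head.** With correlations with the score of 0.40 and 0.60, comparing concordance indices has 47% power on the full score and 32% on the cut score. With 0.40 and 0.65 it is 70% and 47%. Comparing correlations (Williams test) on the full score with a DeLong test on the cut score gives losses of 7 to 29 points over the settings tried.

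**The case against.** Five points can be made for the plan.

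1. *The objective asks whether the assay can diagnose phenotype, and a binary target with an AUROC is the usual tool.* True, but a sample median is not a clinical definition of a severe bleeder: apart from ties, it labels half of any sample severe. The AUROC can stay without being the only measure.

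2. *The uncut score is already analysed.* It is, but one parameter at a time and without factor level among the listed confounders. No planned model of the uncut score contains both FVIII and the NHA parameters.

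3. *No test is named for the NHA, so power is the wrong currency.* This stands in part: the 7-df test is my device. The information loss also applies to estimation. On a common scale, standard errors grow by about 1/√0.637 = 1.25.

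4. *The score may be skewed or pile up at zero.* This stands as a limit on size, and it is why plain linear regression is not the remedy. With more than half the patients at zero, the lowest two quartiles also cannot be separated from the third without breaking ties.

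5. *With 1260 patients a useful assay would be found anyway.* This stands for effects of about 3% to 5% of remaining variance and above.

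Stronger readings go too far. A reader might infer that the protocol gives up a definite 14 to 30 points of power. The documents give no effect size, alpha or score shape, and the loss in the working runs from none to well above 30 points. A reader might also infer that the CAT comparison tests what CAT adds to factor level; it sets each parameter against FVIII. Nor does dependence of the median on case mix favour the remedy, since explained variation and concordance depend on case mix too.

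**Conclusion.** The point holds in a limited form. The protocol itself fixes an unexplained median cut in NHA primary objective 2 and CAT secondary objective 2, and the NHA's increment over FVIII is assessed nowhere else.

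For a near-normal score the cost is about 36% of the information. In power terms this is a fall from 80% to about 57%, or from 90% to about 69%, for a joint test of seven parameters at two-sided alpha 0.05. Those figures are conditional. They approach zero if the NHA explains about 5% of the remaining variance at 1260 patients, and shrink or vanish if half or more of the patients score zero. They are larger when factor level is a strong predictor. The study can run as planned, but the change is worth making because it costs little.

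**What to change.** **Section 6.4.2, primary objective 2.** Make the main added-value analysis a model of the uncut score, fitted with FVIII alone and with FVIII plus the seven NHA parameters. Use an ordinal or rank-based model, which copes with skew and ties at zero, and not plain linear regression. Test the seven parameters jointly, once, and report the optimism-corrected gain in explained variation or concordance, using the bootstrap already planned.

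**Section 6.4.1, secondary objective 2.** Compare each CAT parameter head to head with FVIII by concordance with the uncut score.

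Keep the median-split AUROCs and the NHA calibration plot as descriptive secondary results.

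**Cost.** Rewording of two analysis paragraphs and no extra data. A concordance index is slightly less familiar to clinicians than an AUROC, which stays on display.
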